Treatment objectives for lower risk MDS are to reduce symptoms and improve quality of life. For higher risk MDS, the therapeutic objective is to aggressively modify the natural history of the disease, i.e., to increase survival, and decrease risk of progression to AML. Critical issues in determining therapeutic strategies for patients with MDS include disease heterogeneity, lack of clear pathogenic understanding, tolerability of therapy in the elderly population and a dearth of effective treatments. MDS therapies include: supportive care with transfusion therapy, growth factors (EPO, G-CSF), antibiotics and HMA's (Azacitidine and Decitabine). The only curative therapy for high risk MDS is allogeneic stem cell transplant which has a high morbidity/mortality and therefore not an option for elderly or patients with high comorbidities. Treatment for AML includes induction chemotherapy with cytarabine plus anthracycline, investigational drugs, hematopoietic stem cell transplantation (HSCT), FLT3 and IDH inhibitors in patients whose disease harbor these mutations. Lower intensity regimens using hypomethylating agents (HMA; azacitidine or decitabine) or low-dose cytarabine (LDAC), in combination with venetoclax are now FDA approved for patients over age 75 or younger patients who cannot tolerate cytotoxic chemotherapy.¹ In practice some clinicians will also use HMA/venetoclax for younger patients with diseases known to have a poor response to chemotherapy, such as patients who harbor P53 mutations and patients with MPN's that transform to AML for whom there is currently no universally accepted standard of care. The combination of Azacitidine/venetoclax received FDA approval for AML based the VIALE-A trial which randomized newly diagnosed AML patients older than age 75 or younger patients ineligible for standard induction therapy because of coexisting medical conditions, to Azacitidine/Venetoclax or Azacitidine/placebo and showed an improvement in OS (14.7 vs. 9.6 months), CR (36.7% vs 17.9%) and composite CR (complete remission or complete remission with incomplete hematologic recovery) of 66.4% vs. 28.3%. While the VIALE-A has established Azacitidine/venetoclax as a new standard for some patients > age 75 and for younger patient's ineligible for intensive chemotherapy; a major limitation of this regimen is dose limiting toxicities due to cytopenias requiring dose interruptions and delays leading to increased risk of disease progression. A modification of HMA/ven regimen which can limit dose interruptions due to cytopenias has the

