2.2 Secondary Objective(s)

1. Percentage of MDS participants with complete remission (CR) and complete remission with incomplete marrow recovery (CRi)
2. Percentage of AML participants with complete remission (CR) and complete remission with incomplete marrow recovery (CRi)
- 3.

This will be calculated based on current International Working Group (IWG) criteria. CR is defined as absolute neutrophil count $> 1000/\text{microliter (mCL)}$, platelets $> 100k/\text{mCL}$, red cell transfusion independence, and bone marrow with $< 5\%$ blasts. CRi is defined as bone marrow with less than 5% blasts, and absolute neutrophils of $\leq 10000/\text{mCL}$ or platelets $\leq 100k/\text{mCL}$

4. Event-free survival (EFS)

EFS will be defined as the number of days from randomization to the date of progressive disease, relapse from CR or CRi, treatment failure or death from any cause.

5. Complete remission or complete remission with partial hematologic recovery rate (CR+CRh)

A response of CRh is defined as Bone marrow with $< 5\%$ blasts, peripheral blood neutrophil count $> 0.5 * 10^3/\text{mCL}$ and peripheral blood platelet count $> 0.5 * 10^5/\text{mCL}$.

6. Post baseline transfusion independence rate

Transfusion Independence is defined as a period of 56 days with no transfusion between first dose of study drug and the last dose of study drug + 30 days. The rate of conversion for red blood cells (RBC) and platelets is defined as percentage of participants being post-baseline transfusion independent from baseline transfusion dependence.

7. Rate of Hospitalization

Defined as hospitalization for complication related to myeloid malignancy or treatment. Initial admission for diagnosis or initiation of therapy will not be considered an event.

8. Infection rate requiring hospitalization

Defined as being hospitalized due to an infection or sepsis.

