6.2 General Concomitant Medications and Supportive Care Guidelines

Antimicrobial prophylaxis:

Patients with hematologic illnesses should be offered antimicrobial prophylaxis (antiviral, antifungal, antibacterial) per institutional standards.

Supportive care:

G-CSF can be considered for any patient with < 5% bone marrow blasts who has a baseline ANC < 1.5 x 10⁹/L during the induction phase, but should be held if the most recent ANC is \geq 1.5 x 10⁹/L. During the long-term treatment phase, G-

CSF could be administered for neutropenia (ANC < 1 x 10⁹/L), not felt to be due to active disease.

Concomitant erythropoietin analogues are permitted at physician discretion for transfusion dependent patients with EPO level < 500.

Patients with advanced myeloid malignancies often require frequent clinical visits and CBC evaluation for supportive transfusions. Patients should be monitored as per local standards and treating physicians' standard practice. A weekly CBC at minimum during the induction phase of treatment is suggested.

No antiemetic therapy is required per protocol, but any is permitted at treating physician's discretion.

At higher doses, decitabine is known to cause gastrointestinal toxicity, including constipation. Though not anticipated at provided doses, patients should be monitored and treated as indicated for gastrointestinal toxicity.

The need for central venous access can be determined on a case by case basis, per physician discretion, as central lines carry both benefits and risks to patients. However, decitabine should be given subcutaneously in this setting.

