11.0 MEASUREMENT OF EFFECT

Responses for CR, PR and HI will be described per IWG criteria for MDS and MPN^{23,24}. For AML will use ELN response criteria. Additionally, in order to focus the most objective outcomes, additional MDS/MPN response criteria of spleen response and symptoms response will not be part of the measurement of effect of response, although will be collected as available for descriptive purposes.

Table 2: Criteria for Hematologic Improvement (HI)

Hematologic Improvement (HI)	Response Criteria (Must last at least 8 weeks)
Erythroid Response (pretreatment < 11g/dL)	
 • Hgb increase by \geq g/dL • Relevant reduction of units of RBC transfusions by an absolute number of at least 4 RBC transfusions/8 weeks compared with the pretreatment transfusion number in the previous 8 weeks.
Platelet response (pretreatment, < $100 \times 10^9/L$)	
 • Absolute increase of $\geq 30 \times 10^9/L$ for patients with $> 20 \times 10^9/L$ platelets • Increase from $< 20 \times 10^9/L$ to $> 20 \times 10^9/L$ and by at least 100%
Neutrophil response (pretreatment < $1.0 \times 10^9/L$)	
 • At least 100% increase and an absolute increase $> 0.5 \times 10^9/L$

*Pretreatment values should not be influenced by transfusion, if they are considered transfusion dependent

Table 3: Response criteria for patients with primary diagnosis of MDS²³

Category	Response Criteria (response must last at least 4 weeks)
Complete Remission	
 • Bone marrow: $\leq 5\%$ myeloblasts with normal maturation of all cell lines. (Note persistence of dysplasia) • Peripheral Blood 
 ◦ Hgb $\geq 11\text{g/dL}$ ◦ Platelets $\geq 100 \times 10^9/\text{L}$ ◦ Neutrophils $\geq 1.0 \times 10^9/\text{L}$ ◦ Blasts 0%
Partial Remission	
 • All CR criteria if abnormal before treatment except: 
 ◦ Bone marrow blasts decreased by $\geq 50\%$ over pretreatment but still $> 5\%$ ◦ Cellularity and morphology no relevant
Marrow CR	
 • Bone marrow: $\leq 5\%$ myeloblasts and decrease by $\geq 50\%$ over pretreatment • Peripheral blood: if HI responses, should be noted in addition to marrow CR. (for this protocol, marrow CR absent HI is NOT considered a response)

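### Red-cell transfusion independence and erythroid improvement are scored regardless of erythropoietin-analogue use, and analogue use has no scheduled recording after induction

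*Combined protocol and SAP*

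**What the plan says.** Section 6.2, under supportive care: "Concomitant erythropoietin analogues are permitted at physician discretion for transfusion dependent patients with EPO level < 500." No treatment phase, washout or stable-dose condition is attached.

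Section 2.2, item 6: "Transfusion Independence is defined as a period of 56 days with no transfusion." The period may fall anywhere from the first dose to 30 days after the last. The conversion rate, for red cells and platelets, is the "percentage of participants being post-baseline transfusion independent from baseline transfusion dependence."

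Section 11, Table 2 scores erythroid improvement on a haemoglobin rise or on this transfusion criterion: "Relevant reduction of units of RBC transfusions by an absolute number of at least 4 RBC transfusions/8 weeks." Its footnote, "Pretreatment values should not be influenced by transfusion," guards against transfusion only. Table 3 counts a marrow CR as an MDS response only if hematologic improvement accompanies it.

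The CR wording in Section 2.2 includes "red cell transfusion independence, and bone marrow with" a low blast count, together with neutrophil and platelet thresholds. Tables 3 and 4 (MDS and MDS/MPN) require haemoglobin of at least 11 g/dL for CR. Table 5 (AML) has no haemoglobin or transfusion element.

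Section 13 offers descriptive summaries and mentions no analysis by analogue use. The Section 10 calendar marks concomitant medications at screening and induction, and leaves the long-term and end-of-treatment columns blank.

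**The concern.** An erythropoietin analogue is given to raise red-cell production, and red-cell transfusion independence and erythroid improvement measure red-cell production. A patient who stops needing red cells because an analogue was started meets the definition just as a patient helped by decitabine/venetoclax does. The study has one arm (Section 3.0), so no comparison group can remove the analogue's contribution.

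The affected results are secondary, but the plan leans on them. The cohort-expansion rationale in Section 1.4 cites a transfusion-independence rate of 53% against 26% from a retrospective comparison. Section 13 says the expansion is meant to provide secondary efficacy data for designing later studies. If analogue dates are not collected, the two sources of improvement may not be separable afterwards.

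**Working it through.** **1. Who is exposed.** Section 6.2 covers transfusion-dependent patients with EPO below 500. The red-cell conversion rate is scored in patients who are transfusion dependent at baseline. The first group, when treated, lies largely within the second, but its share is not given.

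**2. Which endpoints can move.**

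| Endpoint | Route for an analogue effect |
|---|---|
| Red-cell transfusion independence (2.2, item 6) | Direct |
| Erythroid improvement (Table 2) | Direct |
| Marrow CR counted as MDS response (Table 3) | Through erythroid improvement |
| CR in 2.2 and Tables 3 and 4 | Red-cell or haemoglobin element only; blasts, neutrophils and platelets must also qualify |
| AML CR in Table 5 | None |
| Platelet transfusion independence | No route in its definition |
| Primary endpoint (dose interruptions) | None |

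**3. What is recorded.** Induction is 12 × 7 = 84 days. A 56-day window starting on day d ends on day d + 55, so it fits inside induction when d is at most 84 − 55 = 29. A window starting on day 30 or later runs into the phase where concomitant medications are not marked. The blanks do not look like an extraction fault: the weight row keeps its end-of-treatment mark after a blank long-term cell, so column positions survived.

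**4. The plan's own figures.** None concerns analogue use. The nearest is the precision of the CR rates, SE = √(p(1−p)/n).
- MDS: √(0.36 × 0.64 / 32) = 8.5%, against a stated maximum of 9%.
- AML: √(0.38 × 0.62 / 38) = 7.9%, against a stated maximum of 8%.
- Simon design (13 then 33 patients), by exact binomial calculation: early termination probability 0.771, alpha 0.047, power 0.809, matching the stated 0.77, 5% and 80%.

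No rule about analogues changes these.

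**5. Possible size (assumed inputs).** Let t be the true rate due to the regimen, f the share of patients who would not otherwise qualify but receive an analogue, and e the share of those who then qualify because of it. The inflation is (1 − t) × f × e. Assume f from 10% to 50% and e from 10% to 40%, so f × e runs from 0.01 to 0.20.

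| t, and its source | Inflation, low | Inflation, high |
|---|---|---|
| 53%, retrospective low-dose cohort (1.4) | 0.47 × 0.01 = 0.5 points | 0.47 × 0.20 = 9.4 points |
| 26%, retrospective standard-dose cohort (1.4) | 0.74 × 0.01 = 0.7 points | 0.74 × 0.20 = 14.8 points |

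The formula leaves out patients the regimen would convert anyway. Multiplying use by an analogue response rate without that allowance would overstate the effect.

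**6. The marrow-CR route.** Section 1.3.4 cites a real-world MDS series on HMA/venetoclax in which 18% had marrow CR without hematologic improvement. If the same share applied here, the inflation of the MDS response rate by this route would be 0.18 × 0.01 = 0.2 points to 0.18 × 0.20 = 3.6 points. In 32 MDS patients that is 32 × 0.036 = 1.2 patients at most under these inputs; one patient is 1/32 = 3.1 points.

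**The case against.** The strongest reply is that analogues are permitted supportive care, and that transfusion independence under the regimen plus permitted care is a legitimate treatment-policy estimand. Removing analogue users would also discard real regimen responders who happened to receive one. This stands, and it is why the all-patient rate should remain the main result. It does not remove the need to show how much of that rate arose with a newly started or increased analogue.

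Other parts also stand. A full 56-day window can fit inside induction, where medications are marked. Adverse-event records (Section 7.2.3) may note a concomitant medication given for an event, though an analogue given for baseline anaemia need not generate one. Section 11 adopts IWG criteria by reference. Whether those sources address growth factors cannot be checked here; the protocol's own tables do not. No hypothesis test or stopping rule uses these endpoints.

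A claim that attribution is left to clinical judgement is weaker. Section 11 asks that treatment, infection and bleeding be considered before a fall in counts is called progression, but asks nothing comparable of a rise.

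A reader might infer more than the text supports:
- That the protocol itself attributes responses to growth factors. Section 1.1.2 says only "MDS therapies include: supportive care with transfusion therapy, growth factors (EPO, G-CSF), antibiotics and HMA's," and Section 6.2 places analogues under supportive care.
- That analogue-eligible patients are exactly the conversion-rate denominator. That rate also covers platelets, and the EPO limit selects a subset.
- That an analogue can produce a CR. It cannot by itself meet the marrow, neutrophil and platelet requirements.

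**Conclusion.** The concern holds as a gap in the secondary erythroid endpoints. Red-cell transfusion independence, erythroid improvement and, through the latter, marrow CR counted as an MDS response are scored without regard to analogue use. No analysis of it is planned, and analogues started after induction have no scheduled capture. Improvement due to an analogue can therefore be credited to the regimen; the documents do not show that it has been.

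The size is unknown. The ranges of 0.5 to 9.4 and 0.7 to 14.8 points rest wholly on the assumed use and response shares, and on borrowing t from the retrospective cohorts. CR is touched only through its red-cell or haemoglobin element in Section 2.2 and Tables 3 and 4, so these ranges overstate any effect on CR. The primary endpoint, Simon design and sample size stand. This is a worthwhile, inexpensive improvement and not a flaw in the main conclusion.

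**What to change.** 1. In the Section 10 calendar, mark concomitant medications in the long-term and end-of-treatment columns, and record analogue start, stop and dose-increase dates.
2. Keep the all-patient rates as the main result.
3. Prespecify in Section 13 a second line for red-cell transfusion independence, erythroid improvement, and marrow CR with erythroid improvement. It counts a response only if no analogue was started or increased in the 8 weeks before the qualifying period or during it. Eight weeks matches the 56-day and 8-week response windows; it is a working choice, not a figure the documents give for analogues. Patients on a stable analogue dose are not excluded.

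Permitted use, visits and sample size do not change. The cost is slightly more data entry and one extra reporting line. That line may be lower than the main rate and may undercount true regimen responders who also received an analogue, so the two should be read together.

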6.3 Criteria for Removal from Study

In the absence of treatment delays due to adverse events, treatment may continue as long as patient is receiving benefit from treatment (see section 6.4), or in the event of the following:

- Disease progression unresponsive to dose adjustment, or progression at maximum dose level
- Intercurrent illness that prevents further administration of treatment,
- The investigator considers it, for safety reasons, to be in the best interest of the subject.
- Any toxicity or adverse event that leads to delay in drug administration of greater than 6 weeks
- Subject decision to withdraw from treatment or from the study

- In accordance with the Declaration of Helsinki and the guidelines of the country of the participating Clinical Study Center, each subject is free to withdraw from the study at any time. An investigator also has the right to withdraw a subject from the study in the event of the patient suffering an intercurrent illness, adverse events, or other reasons concerning the health or well-being of the patient, or in the case of lack of cooperation by the patient. All serious adverse reactions need to be followed until resolution and information returned to study coordinators.
- Should a subject decide to withdraw after administration of study drug, or should the investigator decide to withdraw the subject, all efforts should be made to complete and report the observations up to the time of withdrawal as thoroughly as possible. A final evaluation, the reason for, and the date of withdrawal must be recorded on the CRF. The last visit for each subject will be defined as a study discontinuation/ end-of-study visit, which will occur 30 (± 7 days) days after time of study drug withdrawal.
- Subjects with clinically significant abnormal laboratory values as determined by the investigator or who have ongoing clinically significant treatment related adverse events during their last scheduled clinical evaluation will be monitored and treated until resolution or stabilization is achieved; or, in the event that the subject's condition is not likely to improve because of disease progression, until the cause of the abnormal test result or adverse event can be determined.
- Pregnancy during the course of the study for a child-bearing participant

- Death
- Study chair reserves the right to temporarily suspend or prematurely discontinue this study. The date and reason for discontinuation must be documented. Every effort should be made to complete the appropriate assessments.

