6.4 Duration of Follow Up

The evaluation of the primary and secondary endpoints of ORR, CIR, and DOR are continuous. If in the judgement of patients and the treating clinical team, patients are benefiting from this therapy, the therapy will be continued even after measurement of the primary end-point at week 12 but monitoring will continue every 4 weeks or more often if clinically indicated. Patients will be considered off-protocol monitoring if they develop relapsed or progressive disease.

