Efficacy: The primary end-point of a decrease in dose interruptions will be described as proportion of patients point-estimates, together with the corresponding 95% confidence interval. Kaplan-Meier method will be used to summarize time to event variables.

Secondary end-points and scientific correlative studies: For the secondary end-points and scientific correlates (secondary objectives), either logistic regression or correlation analysis will be utilized to examine and assess the relationships and predictive nature of these biological parameters on hematologic improvement and ability of decitabine/ven to deplete DNMT1 in malignant cells, and the alteration of pyrimidine metabolism. Descriptive summaries of the data will be provided.

Accrual rate: Estimated accrual rate of 1-3 patients per month with approximately 18-24 months to meet total accrual goals, and additional 3 months to observe primary outcome measures. DOR of response will be followed for up to two years, thus a total of three to four years is anticipated to meet all study endpoints.

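### No outcome collection is planned beyond about 30 days after drug stop, although EFS and duration of response need it for patients who stop without an event

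*Combined protocol and SAP*

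**What the plan says.** All references are to the combined protocol and SAP.

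- **Section 6.3** lists reasons for removal from study that need no relapse. They include "Any toxicity or adverse event that leads to delay in drug administration of greater than 6 weeks", intercurrent illness, and "Subject decision to withdraw from treatment or from the study"; the last puts stopping drug and leaving the study in one item. It then says "The last visit for each subject will be defined as a study discontinuation/ end-of-study visit". The timing it gives for this visit is 30 days, plus or minus 7, from the stop of drug. After that visit it asks only for safety follow-up: serious reactions, and significant laboratory values or related adverse events, until they resolve or stabilise.
- **Section 7.4** records adverse events and deaths up to 30 days after the final dose.
- **Section 10** ends its calendar at End of Treatment, and footnote 9 makes that evaluation optional. The three-monthly marrow schedule for two years (footnote 5) is attached to the long-term treatment column.
- **Section 6.4** gives a different end point: "Patients will be considered off-protocol monitoring if they develop relapsed or progressive disease".
- **Section 2.2** defines EFS to the "date of progressive disease, relapse from CR or CRi, treatment failure or death from any cause", with no restriction to time on drug.
- **Section 13** says "DOR of response will be followed for up to two years" and "Kaplan-Meier method will be used to summarize time to event variables". It gives no censoring rule.

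**The concern.** Consider a patient in remission who stops for toxicity, illness or by choice. Section 6.3 gives that patient a last visit about a month later. Section 6.4 can be read as monitoring until relapse or progression, and Section 13 as following the response for up to two years. The endpoints need relapse and death after that month, and no schedule collects them.

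The patient still contributes time up to the last visit, but later events go unseen. Whether that biases the curve depends on whether risk changes after stopping. The protocol's own rationale suggests that it may: Section 1.1.2 links interruptions and delays to progression, and Section 1.2.1 links interruptions to less durable responses. The expansion is meant to supply efficacy data for sizing later trials (Section 1.4, rationale for cohort expansion), so an optimistic EFS or DOR curve would be carried forward.

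**Working it through.** **1. Is longer follow-up built into the plan?** Section 13 gives 18–24 months of accrual and DOR follow-up of up to 24 months. 18 + 24 = 42 months (3.5 years) and 24 + 24 = 48 months (4 years). This agrees with the stated total of three to four years, so the study length does allow for two-year response follow-up.

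**2. Is stopping drug itself an EFS event?** The failure categories in the Section 11 tables are built on death, progression or refractory disease. Stopping drug is not among them, so these patients would be censored rather than counted.

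**3. Size for EFS (illustration).** The documents give no EFS hazard, no stopping rate for this regimen and no hazard after stopping, so all three are assumed:

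- event hazard on drug λ = 0.06 per month
- stopping without an event μ = 0.05 or 0.02 per month
- hazard after stopping kλ, with k = 1, 1.5, 2 or 3
- observation ends 1 month after stopping

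Share stopping event-free by 12 months: μ/(λ+μ) × [1 − exp(−12(λ+μ))] = 33% at μ = 0.05 and 15% at μ = 0.02.

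True EFS: S(t) = exp(−(λ+μ)t) + μ[exp(−kλt) − exp(−(λ+μ)t)]/(λ+μ−kλ).

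Kaplan-Meier with observation cut at stop + 1 month: after month 1 the hazard it sees is λ(1 + kr)/(1 + r), with r = μ[exp(λ+μ−kλ) − 1]/(λ+μ−kλ).

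Example with μ = 0.05, k = 2, t = 12:

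- True: exp(−1.32) = 0.2671 and exp(−1.44) = 0.2369, so S = 0.2671 + 0.05 × (0.2369 − 0.2671)/(−0.01) = 0.418.
- Kaplan-Meier: r = 0.0498, so the hazard is 0.06 × 1.0995/1.0498 = 0.0628 per month after month 1 and slightly lower in month 1. The 12-month estimate is 0.471.

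| Stopping per month | k | True 12-month EFS | Kaplan-Meier | Overstatement (points) |
|---|---|---|---|---|
| 5% | 1 | 48.7% | 48.7% | 0 |
| 5% | 1.5 | 44.8% | 47.9% | about 3 |
| 5% | 2 | 41.8% | 47.1% | about 5 |
| 5% | 3 | 37.6% | 45.7% | about 8 |
| 2% | 1 | 48.7% | 48.7% | 0 |
| 2% | 1.5 | 46.9% | 48.3% | 1.4 |
| 2% | 2 | 45.6% | 48.0% | 2.4 |
| 2% | 3 | 43.6% | 47.4% | 3.8 |

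**4. Size for DOR (illustration).** Section 13 expects CR rates of 36% in 32 MDS and 38% in 38 AML patients: 11.52 + 14.44 = about 26 complete remissions. Assume exponential DOR with a 12-month median, and 24% of responders stopping without relapse within 24 months. The 24% is borrowed from the standard-regimen discontinuation rate for adverse events (Sections 1.2.1 and 13) as a middle scenario only. A simulation with observation ending one month after stopping gives:

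| k | 24-month relapses, full follow-up | Relapses seen | True 24-month DOR | Kaplan-Meier |
|---|---|---|---|---|
| 1 | 19.5 | 16.3 | 0.250 | 0.249 |
| 2 | 20.9 | 16.7 | 0.198 | 0.242 |
| 3 | 21.4 | 17.0 | 0.177 | 0.236 |

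Across median DOR of 9, 12 or 18 months and k of 1 to 3, the share of relapses missed is about 6–10% at 10% stopping, 15–23% at 24% and 26–36% at 40%.

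**The case against.** A last visit is not a censoring rule. A reader might infer that Section 6.3 orders censoring at 30 days. It does not, and no section does. The sentence sits in the item on withdrawal by the subject or investigator, and can be read as a closing treatment and safety visit that matches the 30-day window in Section 7.4. Section 6.4 calls endpoint evaluation continuous, Section 9.1 treats three-monthly marrows as standard of care, and footnote 3 of the calendar counts any blood count collected as efficacy data. This stands as far as it goes: the text is ambiguous, not prescriptive. But none of these places asks anyone to retrieve relapse or death for a patient off drug, so without such data the curve ends near day 30 in practice.

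A reader might also infer that EFS and DOR are certainly overstated. The documents give no hazard after stopping, and the bias is zero if risk does not change. Early tolerability also argues for low stopping: Section 1.4 reports one patient with a held dose and no dose reductions among 17 evaluable patients, although these had completed 12 weeks and are therefore selected. With 32 + 38 = 70 patients, the standard error of 12-month EFS near 42% is √(0.42 × 0.58/70) = 0.059, about 6 points, so most of the gaps above are within sampling error. That is fair, but bias adds to sampling error and does not shrink with more patients.

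Nor does the plan guarantee two years of follow-up for both endpoints. Section 13 gives an upper limit, for DOR only, and DOR is not listed in Section 2.2. The Section 6.4 sentence sits in a paragraph about patients continuing therapy, so it is weak evidence of a rule for those who have stopped.

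**Conclusion.** The inconsistency holds. EFS and DOR need events that the plan does not arrange to collect once drug has been stopped for about 30 days, and Sections 6.3, 6.4, 7.4, 10 and 13 do not agree on when observation ends. The certain consequence is lost information. Overstatement is conditional on a higher risk after stopping: from zero to about 8 points of 12-month EFS at 5% monthly stopping, and zero to about 4 at 2%, under the assumed 6% monthly event hazard.

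Both endpoints are secondary, with no test, power or decision rule attached. The 12-week primary endpoint, the two-stage design and the CR precision targets are untouched. The point should be corrected because the remedy is cheap and these estimates are intended to inform later trials.

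**What to change.** - Separate end of treatment from end of study in Section 6.3, and split withdrawal from treatment from withdrawal from the study. State that the 30-day visit closes treatment and safety visits only.
- For every patient off drug without an event who has not withdrawn consent to follow-up, collect relapse, progression and death from routine records or calls. Continue until an event or the planned limit (up to two years), and state the date from which that limit runs.
- State in Section 13 that EFS and DOR are censored at the last disease assessment or, for death, at last contact, and not at drug stop.
- Reconcile Sections 6.3, 6.4, 7.4, 10 and 13, adding an off-treatment follow-up column to the calendar and keeping the 30-day death window for safety reporting only.

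The cost is an amendment to the wording plus periodic chart or phone status checks. No treatment, visit on drug or sample size changes.
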